7.6 Unscheduled Visit

Unscheduled visits may occur at any time during the study. Any of the following activities may be performed:

- Review concomitant medications (if prior to 28 days after a study vaccination).
- Review adverse events (if prior to 28 days after a study vaccination).

- Review serious adverse events and new-onset chronic medical conditions
- Obtain medical history by interview of subjects and note any changes since the previous visit (if indicated).
- A targeted physical examination may be performed by a study clinician, if indicated based on review of medical history.
- Examine study vaccination site (if within 14 days after a study vaccination).
- Approximately 10 mL of venous blood will be collected for safety labs and performed by the study clinical laboratory (if indicated).

8 STUDY PROCEDURES/EVALUATIONS

8.1 Clinical Evaluations

Subjects will be monitored for local and systemic adverse events during specific protocol-defined post-vaccination periods. As with other aluminum hydroxide-adsorbed vaccines, hypersensitivity reactions would be expected to occur within the first 24 hours after receipt of either of the two vaccines, and other severe local or systemic reactions within 72 hours of vaccination. Subjects will therefore be observed for immediate reactions following each vaccination for at least 1 hour, and will have a clinical assessment either in their home or at the study clinic on Days 1, 3, 7, 14 and 28 following each vaccination. If required, transportation to and from the clinical will be provided. A study clinician will also stay in or near Americaninhas for the duration of the trial and will be available to study subjects at all times. Should a subject call on a study clinician to report an adverse event (AE), it will be fully documented in their study chart, and discussed with the Principal Investigator.

All AEs will be graded for severity and relationship to study vaccine, captured on the appropriate case report form (CRF), and followed to resolution. All Serious Adverse Events (SAEs) will be reviewed by a study physician, recorded on the appropriate SAE form, reported according to applicable regulations and guidelines, and followed through to resolution or stabilization by a study physician. Special attention will also be paid to monitoring for the occurrence of Adverse Events of Special Interest (AESIs), which include inflammatory and autoimmune disorders that may potentially be related to the use of an immunostimulatory adjuvant (although none have been associated with the use of GLA-AF, to date).

A DMID Medical Monitor and a local independent medical monitor will be appointed and a Safety Monitoring Committee (SMC) formed to monitor subject safety and to advise the Principal Investigator and co-investigators on trial-related medical questions or problems. The SMC will periodically review data on safety and enrollment, and will review cumulative safety data for evidence of study related AEs, adherence to the protocol, and factors that may affect outcome or study data such as protocol violations and losses to follow up.

8.2 Laboratory Evaluations

8.2.1 Clinical Laboratory Evaluations

Using standard techniques, the following tests will be performed at the accredited Carlos Chagas clinical laboratory in Governador Valadares, Minas Gerais, Brazil. One or more of the laboratory parameters may be repeated at any time during the study as determined by the PI, if indicated by an AE. A clinically significant abnormal value should be repeated within 14 days if possible and followed up as clinically relevant.

-
1. Complete blood count plus white blood cell differential (WBC, absolute neutrophil count [ANC], hemoglobin concentration and platelet count)
 2. Serum creatinine
 3. Alanine aminotransferase (ALT)
 4. Serum glucose (random)
 5. HBsAg ELISA
 6. HCV antibody assay
 7. HIV ELISA

Urine hCG testing will be performed using urine pregnancy test kits that have been approved by Brazilian and/or US regulatory agencies. Urine dipstick testing will also be performed at the trial sites using an approved product.

8.2.2 Special Assays or Procedures

Anti-*Na*-GST-1 and anti-*Na*-APR-1 (M74) IgG antibody and B cell assays will be performed at the Clinical Immunology Laboratory of the Department of Microbiology, Immunology, and Tropical Medicine (MITM) of the George Washington University; the Dermatology, Allergy, and Clinical Immunology (DACI) Reference Laboratory of Johns Hopkins University; and the University of California at San Francisco. All cryopreservation of plasma, sera and peripheral blood mononuclear cells (PBMCs), as well as screening for levels of IgE against *Na*-APR-1 (M74) and *Na*-GST-1 will take place at the clinical immunology laboratory of CPqRR in Belo Horizonte, Minas Gerais, Brazil. Cryopreservation of sera, plasma and PBMCs will be in liquid nitrogen.

8.2.2.1 Anti-*Na*-APR-1 (M74) and Anti-*Na*-GST-1 Antibody Assays

Antibodies to *Na*-APR-1 (M74) and *Na*-GST-1 will be measured in serum or plasma of study subjects using two different methods for comparison: a) a conventional qualified indirect enzyme-linked immunosorbent assay (ELISA) technique using a Standard Reference Serum; and, b) a custom made ImmunoCAP (Phadia, Inc.) for each antigen (*Na*-GST-1 and *Na*-APR-1 (M74)). Antigen-specific IgG and IgG subclass antibody levels will be measured by ELISA and ImmunoCAP at baseline and at several time-points post-vaccination as outlined in Section 3 and in Appendix B. For the qualified conventional indirect ELISA, 96 microwell plates are coated with purified recombinant *Na*-APR-1 (M74) or *Na*-GST-1, blocked, and incubated with serial dilutions of a positive “standard reference serum” pool to generate a reference curve from which antibody levels of test sera can be interpolated. After washing, a horseradish peroxidase conjugated goat anti-human antibody will be added and incubated with plates, washed again, incubated with a chromogenic substrate, and antibody levels measured on an ELISA plate reader.

Qualified ELISAs (one each for *Na*-GST-1 and *Na*-APR-1 (M74)) will also be used to detect IgE antibodies to each antigen, as screening tests to determine eligibility for study participation. If

during screening for volunteer participation in the study, serum samples with anti-*Na*-GST-1 IgE results by ELISA are greater than the reactivity limit, they will then be tested by the ImmunoCAP method for confirmation. The ImmunoCAP method is considered to be the gold standard for measuring levels of antigen-specific IgE in serum. The ImmunoCAP tests will be performed at the DACI Reference Laboratory of Johns Hopkins University.

Surface Plasmon Resonance (SPR) will be used to measure the affinity of antibody interactions with both recombinant antigens. SPR determines the immunoreactivity and affinity of antibody responses in numerous contexts as it measures rates of antibody-antigen association and dissociation based on the Law of Mass Action to assess antibody affinity.

8.2.2.2 Enzyme Neutralization Assays

In vitro assays have been developed to measure the functional capacity of antibodies induced by vaccination with recombinant *Na*-GST-1 or *Na*-APR-1 (M74) to inhibit or neutralize the activity of the native forms of these proteins. Serum samples collected from study subjects will be tested for their neutralizing capacity at several post-vaccination time points. These assays will be performed at the Clinical Immunology Laboratory of the Department of MITM of the George Washington University

8.2.2.3 Memory B Cell Measurement

The ELISPOT method will be used to evaluate induction of memory B cells (MBCs) after each vaccination and maintenance of MBCs throughout the vaccination schedule to determine if MBCs act as surrogate markers (biomarkers) for later antibody production.

8.2.2.4 Cellular Immunology Assays

Cytokine and chemokine assays will be performed on supernatants from cryopreserved PBMCs collected at various time points in the study, by separating PBMCs from whole blood and culturing cells with media only, the mitogen phytohemagglutinin, the antigens *Na*-APR-1 (M74) or *Na*-GST-1, and crude *N. americanus* antigens extracts (e.g., adult somatic crude antigen extract). Cytokines (e.g., IL-2, IL-4, IL-5, IL-10, TNF α , and IFN γ) will be quantified using Cytometric Bead Analysis kits of supernatants collected from PBMCs stimulated with *Na*-APR-1 (M74) or *Na*-GST-1 antigen for 48 and 72 hours *in vitro*. Chemokines (e.g., RANTES, MIP1a, MCP-1, and IP-10) will be quantified in supernatants using commercially available ELISA kits.

8.2.2.5 Parasitology Assays

Fecal exams will begin with an ether sedimentation assay to determine parasite infection status (positive or negative). Positive samples will undergo Kato Katz fecal thick smear exams to determine infection intensity (eggs per gram of feces).

8.2.3 Specimen Preparation, Handling, and Shipping

8.2.3.1 Instructions for Specimen Preparation, Handling, and Storage

Instructions for specimen preparation, handling, and storage are included in the protocol-specific Manual of Procedures, as appropriate.

8.2.3.2 Specimen Shipment

Specimen shipment will occur at intervals during the course of the study following all applicable International Air Transport Association (IATA) requirements and according to the specifics for storage temperature and documentation as detailed in protocol-specific SOPs, as appropriate.

Specimens for clinical screening and safety laboratory evaluations will be transported from the Americaninhas site to the local (clinical) laboratory.

Specimens for immune responses will be shipped from the Americaninhas site to CPqRR in Belo Horizonte, and then transported to the George Washington University in Washington, DC, in a blinded manner in batches as they become available.

9 ASSESSMENT OF SAFETY

9.1 Specification of Safety Parameters

Safety will be assessed by the frequency and severity of:

1. Study vaccine-related serious adverse events occurring from the time of the first study vaccination through approximately 12 months after the last study vaccination.
2. Solicited Adverse Events – reactogenicity events occurring on the day of each study vaccination through 14 days after each study vaccination:
 - a) Injection site reactions including erythema (redness), induration (hardness)/swelling, pain, and tenderness.
 - b) Systemic reactions including fever, feverishness (chills/shivering/sweating), fatigue (tiredness), malaise (general unwell feeling), myalgia (body aches/muscular pain exclusive of the injection site), arthralgia (joint pain exclusive of the injection site), headache, and nausea.
3. Clinical safety laboratory adverse events occurring from the time of each study vaccination through approximately 14 days after each set of vaccinations. Parameters to be evaluated include WBC, ANC, hemoglobin concentration, and platelet count; ALT; and, creatinine.
4. Unsolicited Adverse Events – non-serious adverse events occurring from the time of the each study vaccination through approximately 28 days after each vaccination.
5. New-onset chronic medical conditions occurring from the time of the first study vaccination through approximately 9 months after the last study vaccination.
6. Adverse Events of Special Interest occurring from the time of the first study vaccination through approximately 9 months after the last study vaccination.

9.2 Methods and Timing for Assessing, Recording, and Analyzing Safety Parameters

9.2.1 Adverse Events

An adverse event (AE) includes any noxious, pathological or unintended change in anatomical, physiological or metabolic functions as indicated by physical signs, symptoms and/or laboratory-detected changes occurring in any phase of the clinical study, whether associated with the study vaccine or placebo, and whether or not considered vaccination related. This includes an exacerbation of pre-existing conditions and intercurrent illnesses.

All AEs will be graded for severity and relationship to study vaccine. A study clinician will be readily available for the duration of the trial to assess AEs. Should a subject call on a study clinician to report an AE, it will be fully documented in their study chart, and discussed with the Principal Investigator.

All AEs will be assessed by the investigator using the following protocol-defined grading system, as or described in Tables 2-5:

Grade 1:	Mild - No effect on activities of daily living; no medical intervention/therapy required
Grade 2:	Moderate - Partial limitation in activities of daily living (can complete $\geq 50\%$ of baseline); no or minimal medical intervention/therapy required
Grade 3:	Severe - Activities of daily living limited to $< 50\%$ of baseline; medical evaluation/therapy required

All AEs will have their possible relationship to study vaccine assessed using the following terms:

Definite:	Clear-cut temporal association, and no other possible cause.
Probable:	Clear-cut temporal association and a potential alternative etiology is not apparent.
Possible:	Less clear temporal association; other etiologies also possible.
Unlikely:	Temporal association between the AE and the vaccine or the nature of the event is such that the vaccine is not likely to have had any reasonable association with the observed illness/event (cause and effect relationship improbable but not impossible).
Not Related:	The AE is completely independent of vaccine administration; and/or evidence exists that the event is definitely related to another etiology.

The degree of certainty with which an AE can be attributed to administration of study vaccine will be determined by how well the event can be understood in terms of one or more of the following:

1. The event being temporally related with vaccination or reproduced on re-vaccination.
2. A reaction of similar nature having previously been observed with this type of vaccine and/or formulation.
3. The event having often been reported in the literature for similar types of vaccines.

9.2.2 Reactogenicity

Reactogenicity events are AEs that are known to occur with types of vaccine similar in composition to those being tested in this study. The following Toxicity Grading Scales will be used to grade solicited local (injection site) and systemic (subjective and quantitative) reactions:

Table 2: Assessment of Solicited or Expected Adverse Event Severity

Adverse Event	Grade	Severity
Pain at injection site	1	Easily tolerated, does not interfere with activity
	2	Repeated use of non-narcotic pain reliever for > 24 hours or interferes with daily activity
	3	Any use of narcotic pain reliever or prevents daily activity
Tenderness at injection site	1	Mild discomfort to touch
	2	Discomfort with movement
	3	Significant discomfort at rest
Erythema at injection site	1	25 mm – 50 mm
	2	51 mm – 100 mm
	3	> 100 mm
Induration/swelling at injection site	1	25 mm – 50 mm and does not interfere with daily activity
	2	51 mm – 100 mm or interferes with daily activity
	3	>100 mm or prevents daily activity
Fever (oral)	1	38.0°C – 38.4°C
	2	38.5°C – 38.9°C
	3	>39.0°C
Headache	1	Easily tolerated, does not interfere with daily activity
	2	Repeated use of non-narcotic pain reliever for >24 hours or interferes with daily activity
	3	Any use of narcotic pain reliever or prevents daily activity
Nausea	1	Easily tolerated, does not interfere with daily activity
	2	Interferes with daily activity
	3	Prevents daily activity
Vomiting	1	1-2 episodes in 24 hours and does not interfere with activity
	2	> 2 episodes in 24 hours or interferes with daily activity
	3	Prevents daily activity or requires outpatient IV hydration
Myalgia	1	Easily tolerated, does not interfere with daily activity
	2	Interferes with daily activity
	3	Prevents daily activity
Arthralgia	1	Easily tolerated, does not interfere with activity
	2	Interferes with daily activity
	3	Prevents daily activity
Urticaria	1	Requiring no medications
	2	Requiring PO or topical treatment, or IV medication or steroids for <24 hours
	3	Requiring IV medication or steroids for >24 hours
Mucocutaneous Reaction / Rash	1	Erythema; pruritus or localized macular rash
	2	Diffuse, maculopapular rash, dry desquamation
	3	Vesiculation or moist desquamation or ulceration

Table 3: Assessment of Unsolicited Systemic Adverse Event Severity

Systemic AE	Mild (Grade 1)	Moderate (Grade 2)	Severe (Grade 3)
Anorexia	Loss of appetite without decreased oral intake lasting greater than 48 hours	Loss of appetite associated with decreased oral intake without significant weight loss	Loss of appetite associated with significant weight loss
Diarrhea	3 loose stools/24 hours	4-5 loose stools/24 hours	>6 loose stools or requires outpatient IV hydration
Constipation	Not Applicable	Persistent constipation requiring regular use of dietary modifications, laxatives, or enemas	Obstipation with manual evacuation indicated
Fatigue	No interference w/activity	Some interference w/activity	Significant, prevents daily activity
Arthritis	Mild pain with inflammation, erythema or joint swelling – but not interfering with function	Moderate pain with inflammation, erythema or joint swelling – interfering with function, but not with activities of daily living	Severe pain with inflammation, erythema or joint swelling –and interfering with activities of daily living
Vasovagal episode (associated with a procedure of any kind)	Present without loss of consciousness	Present with transient loss of consciousness	Not Applicable
Vertigo	Causes no or minimal interference with usual daily activities	Causes greater than minimal interference with usual daily activities	Inability to perform daily activities
Cough	Transient- no treatment	Persistent cough; treatment responsive	Paroxysmal cough; uncontrolled with treatment
Bronchospasm, Acute	Transient; no treatment; 70% - 80% FEV ₁ of peak flow	Requires treatment; normalizes with bronchodilator; FEV ₁ 50% - 70% (of peak flow)	No normalization with bronchodilator; FEV ₁ 25% - 50% of peak flow; or retractions present
Dyspnea	Dyspnea on exertion	Dyspnea with normal activity	Dyspnea at rest
Hypersensitivity	Transient flushing or rash	Rash; flushing; urticaria; dyspnea	Symptomatic bronchospasm, with or without urticaria; parenteral medications(s) indicated; allergy-related edema/angioedema; hypotension

Table 4: Assessment of Basic Body Function Adverse Event Severity

Vital Signs*	Mild (Grade 1)	Moderate (Grade 2)	Severe (Grade 3)
Tachycardia – beats per minute	101-115	116-130	>130
Bradycardia – beats per minute	50-54	45-49	<45
Hypertension** (systolic, mm Hg)	141-150	151-155	>155
Hypertension** (diastolic, mm Hg)	91-95	96-100	>100
Hypotension** (systolic, mm Hg)	85-89 (and symptomatic)	80-84 (and symptomatic)	<80
Respiratory Rate – breaths per minute	18-20	21-25	>25

*Subject should be at rest for measurement of vital signs

**With repeat testing at same visit

Table 5: Assessment of Laboratory Adverse Event Severity

HEMATOLOGY	Grade 1 (Mild)	Grade 2 (Moderate)	Grade 3 (Severe)
Hemoglobin Males Females	11.0 – 12.0 g/dL 10.3 – 11.3 g/dL	9.5 – 10.9 g/dL 8.5 – 10.2 g/dL	<9.5 g/dL <8.5 g/dL
Platelets	110,000 – 130,000/mm ³	90,000 – 109,999/mm ³	<90,000/mm ³
WBCs (increase)	10,800 – 15,000/mm ³	15,001 – 20,000/mm ³	<20,000/mm ³
WBCs (decrease)	2300 – 3200/mm ³	1400 – 2299/mm ³	<1400/mm ³
ANC (decrease)	750 – 1000/mm ³	500 – 749/mm ³	<500/mm ³
CLINICAL CHEMISTRIES	Grade 1	Grade 2	Grade 3
Serum creatinine Males Females	1.5 – 1.7 mg/dL 1.5 – 1.7 mg/dL	1.8 – 2.0 mg/dL 1.8 – 2.0 mg/dL	>2.0 mg/dL or requires dialysis >2.0 mg/dL or requires dialysis
ALT Males Females	58 – 115 U/L 64 – 128 U/L	116 – 230 U/L 129 – 255 U/L	>230 U/L >255 U/L

All local (injection-site) reactions occurring within the first 7 days after vaccination will be considered definitely related to vaccination.

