9.5 Halting Rules

If a dose of study vaccine is considered significantly reactogenic (see below and Section 9.2.2), dose escalation and/or additional vaccinations will be suspended until reviewed by the SMC, Independent Safety Monitor, DMID Medical Monitor, and IND sponsor (SVI). Any recommendation of the Independent Safety Monitor, DMID Medical Monitor, and SMC to resume or suspend further injections (either for an individual subject, an entire Group, or the full study) will be communicated in writing to the sponsor and Principal Investigator. All communications from the SMC will subsequently be forwarded by the investigators to the IRBs.

The following criteria will be used to define significant reactogenicity:

- One or more participants experience a protocol defined SAE that is determined to be possibly, probably, or definitely related to a study vaccine, **OR**,
- One or more participants experience a protocol defined AESI that is determined to be possibly, probably, or definitely related to a study vaccine, **OR**,
- One or more participants experience a protocol defined Grade 3 hypersensitivity reaction that is possibly, probably or definitely related to a study vaccine, **OR**,
- Two or more participants experience a protocol defined Grade 2 hypersensitivity reaction that is probably or definitely related to a study vaccine, **OR**,
- One or more participants in a single Group (i.e., Group 1, Group 2, etc.) experience the same objective physical finding or laboratory abnormality of Grade 3 or higher (with the exception of isolated Grade 3 erythema or swelling), that is determined to be probably or definitely related to a study vaccine, **OR**,
- Two or more participants in a single Group experience the same Grade 2 or higher safety laboratory abnormality or Grade 3 clinical AE that is possibly, probably or definitely related to a study vaccine.

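### Section 9.2.2 grades the same urticaria one grade apart in two tables, the 9.5 hypersensitivity halting rules do not say which row governs, and the Table 5 Grade 3 cell for raised WBC has the wrong sign

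*Protocol*

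**What the plan says.** Protocol Section 9.2.2 has two rows that can grade hives.

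- **Table 2 (solicited or expected events), Urticaria row**, graded by treatment. Grade 1: "Requiring no medications". Grade 2: "Requiring PO or topical treatment, or IV medication or steroids for <24 hours". Grade 3: "Requiring IV medication or steroids for >24 hours".
- **Table 3 (unsolicited systemic events), Hypersensitivity row.** Grade 1 covers only transient flushing or rash. Grade 2: "Rash; flushing; urticaria; dyspnea", with no treatment criterion. Grade 3 includes "parenteral medications(s) indicated", with no duration.

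Two halting rules in Section 9.5 use these grades:

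- "Two or more participants experience a protocol defined Grade 2 hypersensitivity reaction that is probably or definitely related to a study vaccine"
- "One or more participants experience a protocol defined Grade 3 hypersensitivity reaction that is possibly, probably or definitely related to a study vaccine"

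Neither rule names a table or row. The lead-in to 9.5 reads "If a dose of study vaccine is considered significantly reactogenic (see below and Section 9.2.2", and the parenthesis closes there. Section 9.2.2 holds both tables.

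Table 5, also in 9.2.2, grades a raised WBC as 10,800–15,000/mm³ (Grade 1), 15,001–20,000/mm³ (Grade 2) and <20,000/mm³ (Grade 3). Under 9.5, one Grade 3 laboratory abnormality in a Group, probably or definitely related, suspends vaccination. Under 5.3.3, a Grade 3 laboratory value that does not fall to Grade 2 or below is a reason not to give dose 2 or 3.

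**The concern.** A halting rule fixed in advance should give the same answer whoever fills in the form. Here the same case of hives can carry two grades, and each one-grade difference crosses a threshold in 9.5. Section 4 stops progression to the next dose Group when a 9.5 criterion is met, so the choice of row can also decide whether escalation proceeds.

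The event matters at this site. Section 2.1.3 reports that several volunteers in the lowest-dose cohort of an earlier hookworm vaccine trial there had widespread urticaria soon after vaccination, and that vaccinations were halted. Section 2.2.2 adds that *Na*-APR-1 (M74) has not yet been given to people in an endemic area.

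The WBC cell is a separate and simpler fault: a threshold that feeds a safety rule is wrong as printed.

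**Working it through.** **1. Urticaria, row against row.** The trigger columns apply each row's grade to the two hypersensitivity rules in 9.5.

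| Treatment | Table 2 grade | Table 3 grade | Cases to suspend, Table 2 | Cases to suspend, Table 3 |
|---|---|---|---|---|
| None | 1 | 2 | no fixed trigger | 2 |
| Oral or topical | 2 | 2 | 2 | 2 |
| IV <24 h | 2 | 3 | 2 | 1 |
| IV >24 h | 3 | 3 | 1 | 1 |

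Two of the four situations conflict, and both change the trigger. Reading the Table 3 Grade 2 list as a required combination would not remove the conflict, because Grade 1 of that row does not cover urticaria. The relatedness condition also moves with the grade: Grade 2 cases must be probably or definitely related, while Grade 3 cases count if possibly related.

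The other fixed clinical triggers in 9.5 need a Grade 3 event, an SAE or an AESI. Untreated urticaria recorded as Grade 1 would therefore reach suspension only through judgment.

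**2. How often two cases would arise.** Inputs: N = 60 (Section 5) and a per-subject rate p of related urticaria of the given type that is not confined to the injection site. The protocol gives no such rate for these vaccines. Section 2.1.10 gives 0.1% for hepatitis B vaccine. The 1% and 3% rates are assumptions, taken from the illustrative rates in 11.2.

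P(≥1) = 1 − (1−p)^60

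P(≥2) = 1 − (1−p)^60 − 60p(1−p)^59

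Check against the N = 60 column of 11.2: P(≥1) is 45.28% at 1% and 83.92% at 3%. Both match the printed values.

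| p | P(≥1) | P(≥2) |
|---|---|---|
| 0.1% (hepatitis B vaccine) | 5.83% | 0.17% |
| 1% (assumed) | 45.28% | 12.12% |
| 3% (assumed) | 83.92% | 54.08% |

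For untreated urticaria, the P(≥2) column is the chance that the fixed rule fires under Table 3; under Table 2 it is zero. For IV treatment under 24 hours, the contrast is P(≥1) under Table 3 against P(≥2) under Table 2. That second contrast is only indicative, because it uses one p for two rules with different relatedness conditions.

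**3. WBC increase.**

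| Count (/mm³) | As printed | With >20,000 |
|---|---|---|
| 6,000 | Grade 3 | none |
| 12,000 | Grades 1 and 3 | Grade 1 |
| 18,000 | Grades 2 and 3 | Grade 2 |
| 25,000 | none | Grade 3 |

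The relatedness condition in 9.5 would screen out a normal count. The dosing bar in 5.3.3 has no such condition.

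**The case against.** The strongest reply is that 9.5 is close to determinate. It speaks of hypersensitivity reactions, and only one row in the protocol has that name. Section 2.3.1 counts urticaria among immediate hypersensitivity reactions. The solicited list in 9.1 omits urticaria, which points to the table for unsolicited events. The citation of 9.2.2 is attached to the phrase about reactogenicity, not to the hypersensitivity rules. This stands as far as it goes: Table 3 is the natural reading, and the ambiguity is narrow.

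It does not close the gap. Table 2 also covers expected events and has a row named Urticaria, which a clinician grading hives could reasonably use. Nothing says that such a grade must be re-derived for halting. The table titles do not settle it either: 9.1 lists fatigue as solicited, yet fatigue is graded in Table 3.

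Judgment is a real back-up. The Independent Safety Monitor may hold the study at any time (9.5), and the monitors or the SMC may stop escalation on clinical grounds (Section 4). IgE screening (2.3.2 and 5.2) should also lower the risk. These limit the harm, but they do not replace a rule written to work without judgment.

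A reader might infer that the conflict also runs the other way, with oral steroids for more than 24 hours being Grade 3 in Table 2 and Grade 2 in Table 3. The text does not support this well. Table 2 names oral treatment separately, so IV most naturally governs both medication and steroids. Even on the wider reading, a Grade 3 urticaria could suspend on one case through the 9.5 rule on objective physical findings.

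On WBC, the reply is that this is a typing slip with obvious intent. That is so: the row is labelled as an increase and Grade 2 ends at 20,000. It still needs correcting, because a form or edit check programmed from the table would carry the error.

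**Conclusion.** The point holds as an inconsistency in safety wording, with two certain grading conflicts (untreated, and IV for under 24 hours) and one wrong sign. If a case is graded in Table 2 and that grade is carried into 9.5, two untreated cases meet no fixed trigger instead of suspending vaccination, and brief IV treatment needs two cases instead of one.

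How often this would matter cannot be fixed from the protocol. The chance of two or more cases in 60 runs from 0.17% at the only urticaria rate quoted, which is for another vaccine, to 12.1% and 54.1% at assumed rates of 1% and 3%. The assumed rates are applied whole to one treatment type, so they are illustrations and not forecasts.

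Three stronger inferences are not supported. The protocol is not without a rule for urticaria, since Table 3 is the likelier reading. It cannot be said that the earlier trial's cases would have escaped the rule, because the protocol does not say how they were treated. And it is unlikely that anyone would grade a normal WBC as a severe increase.

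**What to change.** - In 9.5, state that the Table 3 Hypersensitivity row governs the hypersensitivity halting rules, and that vaccine-related urticaria not confined to the injection site is graded by that row.
- In Table 2, either align the Urticaria row with it (untreated = Grade 2; parenteral medication indicated = Grade 3) or limit the row to injection-site hives. This is better than counting the higher of the two grades, which would leave two severity grades for one event in the primary safety outcomes.
- In Table 5, change the Grade 3 cell for raised WBC to >20,000/mm³.

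The injection-site limit is worth stating because 9.2.2 treats every local reaction in the first 7 days as definitely related, and the hypersensitivity rules are not confined to a single Group. Without it, two trivial local cases among 60 subjects could be argued to suspend the study.

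The cost is a few lines of text, one table row, one sign and the matching CRF grading note, with no added subjects or data. If sites would otherwise have used Table 2, the chance of a temporary suspension pending SMC review rises somewhat. If 9.5 already means Table 3, the halting triggers for hypersensitivity do not change.
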